12.2. Statistical Analysis Plan

12.3. General considerations

intent-to-treat population , defined as all participants who are randomized to treatment. With the exception of the Primary Efficacy Endpoint Analysis, percentage responders to

the intention-to-treat population, missing data will not be estimated or carried forward in any statistical analyses.

All comparisons of treatment groups will be performed using two-tailed tests at a significance level of 0.05 ($p < 0.05$). The null hypothesis for all analyzes is that there is no difference between treatment groups.

All summaries, statistical analyzes and individual participant registration data described below will be provided in separate attachments. Separate listings will be provided for each of the treatment groups in the intent-to-treat population.

12.4. Disposition of Participants

Summaries of the number of patients randomized, number completing the study, and incidence of protocol violations will be provided for each treatment group. The number (%) of participants with protocol violations that may affect the study objectives will be based on database analysis. This assessment will be made prior to determining the treatment allocation for all participants in the database.

12.5. Demographic Characteristics and Disease

The statistical analyzes described below will be completed for:

- The participating intent-to-treat population;
- The evaluable population of efficacy.

Demographic Characteristics

The table below identifies the demographic and disease characteristics used to determine the comparability of treatment groups and the methods used to analyze them.

Table 1 - Variables analyzed to determine comparability

Variable	Analysis method
Baseline age	One-way ANOVA/KW
baseline CV	One-way ANOVA/KW
basal CD4+	One-way

	ANOVA/KW
--	----------

The primary efficacy endpoint is the number (%) of participants who met the primary endpoint (HIV-1 RNA Viral Load <50 copies/ml) at the week 48 visit (or discontinuation). Participants will be counted as non-responders if they do not show up by Week 48 (or termination).

The DTG treatment group will be compared to the EFV group with respect to the percentage of responders using a chi-square test. Two-tailed 95% confidence intervals for the percentage of responders will be calculated for each treatment group.

The following table identifies secondary efficacy endpoints and the methods used to analyze them.

Table 2 - Variables analyzed at the main points of analysis

Variable	Analysis method
Frequency of Adverse Events	Chi-square test
Proportion of participants achieving CV <50 copies/ml at each analysis point	Chi-square test
proportion of deaths	Chi-square test
CD4+ count at each analysis point	One-way ANOVA/KW

12.6. security endpoints

Summaries and statistical analyzes of safety endpoints will be completed for the intention-to-treat population. The incidence of at least one grade III or IV event will be the primary safety endpoint of the study. Treatment groups will be compared with respect to the percentage of participants with at least one grade III or IV adverse event using a Chi-square test.

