1.1. Primary

- To assess early (all-cause) mortality rates within the first year of treatment in participants symptomatic with AIDS who started antiretroviral therapy with regimens based on Dolutegravir (DTG) or Efavirenz (EFV).

1.2. secondary

- Evaluate the proportion of participants with suppression of plasma viremia (CV less than 50 copies/ml), at different times of the study;
- Compare CD4+ gain over time for both groups;
- Compare the frequency of adverse events in participants using regimens with DTG and EFV.

2. Clinical Hypotheses

- DTG-based regimens are most effective in rapidly recovering CD4+ cells within the first year of therapy;
- DTG-based antiretroviral regimens are able to promote more rapid suppression of HIV plasma viremia than EFV;
- The group of participants treated with DTG-based regimens will have a lower rate of early mortality than those treated with the comparator drug.

3. Background and Justification

Currently available antiretroviral agents (ARVs) have made it possible to successfully treat virtually all HIV-infected participants, but some problems related to early mortality are still a matter of concern, especially in countries with limited resources (1,2). There are several reports showing that these participants have a significantly higher risk of death during the first few months of treatment compared to results observed in developed countries (3-11). One of the consistently detected risks for early mortality across these reports is low baseline CD4+ counts, although it does not appear to be the only reason for such an outcome. Other factors associated with higher mortality rates for participants starting antiretroviral therapy (ART) are anemia, low body weight, and ongoing opportunistic infections (12,13). Mortality rates for participants starting

antiretroviral therapy are quite variable, ranging from 1.8%, as demonstrated by a study carried out in Baltimore/USA, to values as high as 54%, in some areas of the African continent (3- 13).

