12.1. Sample Size Justification

Mortality rates are quite variable, depending on region, specific study, and population.

Most studies from African countries have shown that mortality in the first 3 months of ART for participants with CD4+ cells under the threshold of 50 cells/mm³ is generally greater than 30%, and may reach 52% in some reports.

On the other hand, in developed countries, most deaths in such a population usually occur after 7 months of therapy and the mortality rate is just as low (1.8% for the first year of treatment).

We estimated that early mortality for participants included in the EFV arm would be similar to the rates detected in African countries (around 30%). We hypothesize that participants using DTG-based regimens would benefit from faster recovery of CD4+ cell count and that they behave like those individuals starting antiretroviral therapy in developed countries (mortality rate around 2%).

Considering a lower limit of 2% (DTG arm) and an upper limit of 25% (EFV arm), a 95% CI and 80% power to detect differences between groups, it would be necessary to treat a total of 84 participants (42 on each arm). Adding 10% for dropouts, this would result in a total of 92 subjects (46 in each arm).

With the recent changes in treatment recommendations, all 92 participants will receive DTG. Participants who used EFV will be retrospectively evaluated, through the review of medical records, in an identical number (92 participants).

This will be an exploratory pilot study.

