## **Statistical Analysis Plan**

### **General Considerations**

All abstracts and statistical analyzes will be provided for the intended **intention to treat population**, defined as all participants who are randomized to treatment. With the exception of the Primary Efficacy Parameter Analysis, percentage of responders for the intent-to-treat population, missing data will not be estimated or transported in any statistical analyzes.

All comparisons of treatment groups will be performed using two-tailed tests at a significance level of 0.05 ( $p < 0.05$ ). The null hypothesis for all analyzes is that there is no difference between the treatment groups.

All abstracts, statistical analyzes and individual record data of participants described below will be provided in separate annexes. Separate listings will be provided for each of the treatment groups in the intention-to-treat population.

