### **Arrangement of participants**

Summaries of the number of randomized patients, number of those completing the study, and incidence of protocol violations will be provided for each treatment group. The number (%) of participants with protocol violations that may affect study objectives will be based on database analysis. This evaluation will be done before determining the allocation of treatment for all participants in the database.

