**Table 2 - Variables analyzed in the main points of analysis**

Variable	Analysis method
Frequency of Adverse Events	chi-square test
Proportion of participants achieving VL <50 copies / ml at each point of analysis	chi-square test
Proportion of deaths	chi-square test

CD4 + count at each point of analysis	One-way ANOVA/KW
---------------------------------------	------------------

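### No participant is randomised, yet the analysis set is defined by randomisation and every DTG–EFV comparison is unadjusted, so confounding cannot be told apart from a drug effect

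*Protocol*

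**What the plan says.** Protocol section 4 describes an open-label pilot with prospective follow-up on DTG and a chart review of patients who used EFV. Section 12.1 confirms it: "With the recent changes in treatment recommendations, all 92 participants will receive DTG", with 92 EFV records as the comparator.

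The analysis text does not follow that design:

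- The intention-to-treat set is "defined as all participants who are randomized to treatment" (SAP, General Considerations; same definition in Protocol 12.3).
- Protocol violations are to be reviewed before group membership is established: "This assessment will be made prior to determining the treatment allocation for all participants in the database" (Protocol 12.4), and in the SAP "This evaluation will be done before determining the allocation of treatment for all participants in the database" (Arrangement of participants).
- For efficacy, "The DTG treatment group will be compared to the EFV group with respect to the percentage of responders using a chi-square test" (Protocol 12.5). Table 2 of both documents gives chi-square for viral load below 50, adverse events and deaths ("Proportion of deaths" in the SAP), and one-way ANOVA/KW for CD4+. Grade III/IV events and laboratory abnormalities are also compared by chi-square (Protocol 12.6 and 12.7).
- Table 1 compares baseline age, viral load and CD4+ between groups. Neither document says what follows from an imbalance.

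The hypothesis at stake is in Protocol section 2: "The group of participants treated with DTG-based regimens will have a lower rate of early mortality than those treated with the comparator drug".

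**The concern.** A chi-square test of two groups tests a treatment effect only if the groups would have had the same risk without the treatment difference. Randomisation would support that; a prospective cohort set against historical charts does not. Here treatment, calendar period and method of data collection all change together.

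Protocol section 3 itself names anaemia, low body weight and active opportunistic infection as drivers of early death. None is in Table 1, and none enters any comparison.

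The groups are also assembled somewhat differently. DTG participants need consent before any procedure (7.2), while no consent form applies to the charts (10.1), so very early deaths may be captured differently. Section 10.1 accepts EFV baseline laboratory results up to 90 days old, while 7.2 requires a DTG viral load within 30 days.

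The unadjusted p-value is the only test the plan offers of its mortality hypothesis. A difference in baseline severity could create or hide an apparent DTG benefit, and no planned step would reveal which.

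**Working it through.** **1. The plan's own figure.** Inputs from Protocol 12.1: 2% against 25% mortality, 80% power; two-sided 5% from 12.3.

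- Mean rate: (0.02 + 0.25)/2 = 0.135.
- Uncorrected: n = [1.96·√(2·0.135·0.865) + 0.8416·√(0.02·0.98 + 0.25·0.75)]² / 0.23² = 33.4, so 34 per arm.
- Continuity-corrected: (33.4/4)·[1 + √(1 + 4/(33.4·0.23))]² = 41.7, so 42 per arm. This matches the plan.
- Dropout: 84 × 1.10 = 92.4, stated as 92.

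The arithmetic is sound. It belongs to a two-arm comparison and carries no allowance for confounding. At 92 per group, exact power for 2% against 25% exceeds 99.8% with or without the correction.

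**2. False positives from one unbalanced risk factor.** The 92 per group is from the protocol; everything else here is assumed. DTG has no effect, mortality is 8% without the factor, and the factor multiplies it by RR. Group mortality = 0.08 × (p·RR + 1 − p), where p is the factor's prevalence. For RR 3 and 40% against 60%: DTG 0.08 × (0.40·3 + 0.60) = 14.4%; EFV 0.08 × (0.60·3 + 0.40) = 17.6%. Rejection probabilities are exact binomial sums over all pairs of death counts.

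| RR | Prevalence DTG / EFV | Mortality DTG / EFV | Rejection, 5% chi-square | With continuity correction |
|---|---|---|---|---|
| 3 | 45% / 45% | 15.2% / 15.2% | 4.9% | 3.1% |
| 3 | 45% / 55% | 15.2% / 16.8% | 5.9% | 3.9% |
| 2 | 40% / 60% | 11.2% / 12.8% | 6.3% | 3.7% |
| 3 | 40% / 60% | 14.4% / 17.6% | 8.9% | 6.2% |
| 3 | 30% / 60% | 12.8% / 17.6% | 14.6% | 10.7% |
| 4.3 | 30% / 60% | 15.9% / 23.8% | 26.8% | 21.6% |

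The excess is one-sided. In the RR 3, 40%/60% row, 8.4 of the 8.9 points falsely favour DTG, against about 2.5 when balanced. Swapping the groups gives the same rates against DTG. With 5% or 12% base mortality, the RR 3, 30%/60% row becomes 10.7% or 21.3%.

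**3. The plan's EFV rate.** Take 25% EFV mortality (12.1), no DTG effect, and an assumed background mortality in the DTG cohort. The uncorrected test rejects in 5.1% of trials at 25%, 12.7% at 20% and 39.6% at 15%.

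**4. Viral-load response.** If suppression is 60% on EFV (assumed) and the DTG cohort would differ by 5 or 10 points for reasons other than the drug, the chi-square rejects in 10.9% or 30.1% of trials. From 70%, the figures are 12.0% and 35.0%.

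**5. Masking.** Suppose DTG truly halves mortality and the RR 3 factor is present. With 50% prevalence in both groups, mortality is 8.0% against 16.0% and power is 39.0%. With 60% in DTG and 40% in EFV, it is 0.5 × 0.08 × 2.2 = 8.8% against 0.08 × 1.8 = 14.4%, and power is 22.0%.

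**6. Does adjustment work?** In 20,000 simulated trials for each imbalanced null case in step 2, propensity weighting on the measured factor with a robust variance rejects in about 4 to 5%. Effective size is about 82 to 91 of 92 per group. This covers a measured factor only.

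**The case against.** The strongest reply has five parts.

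- **Exploratory pilot.** Section 12.1 uses that label. But the plan still states a directional mortality hypothesis, a power calculation and two-sided 5% tests, and the label supplies no adjustment.
- **Shared eligibility.** Both groups need CD4+ of 50 or less, viral load of at least 1,000 and symptoms, and section 11 requires consecutive selection. This narrows CD4+ differences but not anaemia, weight, opportunistic infection or era. The contrast in entry conditions is also weaker than it first looks: 7.2 lets a legal representative consent, and 7.1 requires the EFV viral load to be immediately before therapy.
- **Small, assumed bias.** The imbalances in step 2 are not from the documents, two corrected rates stay below 5%, and the spurious gaps (1.6 to 7.9 points) are far below the planned 23. This stands: a true 2% against 25% result would not be explained by these examples. But that contrast is itself an assumption, and a smaller observed difference could not be interpreted.
- **Leftover wording.** The intended analysis set can be guessed from 12.1. That is fair, but the correction is still needed, and the unadjusted tests remain whatever the set is called.
- **Partial remedy at a higher cost.** Adjustment cannot remove era. Weighting on five covariates may also cost more than the one-factor examples: with five independent covariates each shifted by 0.3 or 0.4 SD, effective size averages about 78 or 69, with much lower values in single trials. This stands as a caution on cost. It argues for a short covariate list and a cautious claim, not for leaving the comparison unadjusted.

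**Conclusion.** The concern holds. Nobody is randomised, the analysis set as defined contains no one, and neither document has regression, matching, weighting, stratification or a sensitivity analysis for confounding. Followed exactly, the plan gives a confounded test of its own mortality hypothesis. This is an error in the plan as written rather than a missing detail, and it should be corrected before outcomes are compared.

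The size of the harm is conditional. Under the step 2 assumptions, the false-positive rate runs from near nominal under mild imbalance to 26.8% (21.6% corrected) under the strongest one shown. A real halving of mortality can lose nearly half its power. The documents do not show which way the cohorts differ.

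**What to change.** 1. **Analysis set.** Include all eligible participants who started DTG prospectively, and all consecutive eligible patients who started EFV as first therapy in one stated calendar window with a stated counting start, regardless of later data. Reconcile 2014–2016 (Protocol section 4) with 2013–2016 (7.1). Remove the randomisation and treatment-allocation wording from Protocol 12.3 and 12.4 and the matching SAP sections.
2. **Main comparison.** Pre-specify one parsimonious adjusted analysis of one-year mortality (6.1), and the same for week-48 viral-load response (12.5). One example is propensity-score weighting on baseline age, CD4+, log10 viral load, haemoglobin, and opportunistic infection where the medical history gives it. Keep the unadjusted chi-square as supportive. Body weight is in neither visit table, so add it only if the charts hold it.
3. **Conclusion.** Report a non-randomised association. State that treatment era is fully confounded with treatment and cannot be adjusted away.

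**Cost.** SAP wording and modest programming. Age, CD4+, viral load and haematology are already baseline data in both groups; opportunistic infection must be extracted from the history. Some effective sample size is lost, possibly more than in the one-factor examples. The adjusted mortality estimate will be imprecise, because the plan's rates imply about 0.02 × 92 = 1.8 DTG deaths against 0.25 × 92 = 23 EFV deaths. The claim will be more cautious.

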12.7. Serious Adverse Events

Secondary safety endpoints are the incidence of adverse events categorized according to preferred term and body system, clinically significant laboratory test results, and changes in vital signs. Treatment groups will be compared with respect to the percentage of participants with clinically significant laboratory test results at Week 4, 8, 16, 24, 36, or 48 visits using Chi-square.

Summaries of physical examination data, vital signs (actual value and change from baseline), and laboratory data (actual value and change from baseline) will be provided at each visit.

12.8. Report of Adverse Experiences

The investigator and the site team will be responsible for documenting, detecting and reporting events that meet the definition of Adverse Event is defined as any unwanted medical event occurring in a participant or individual involved in a clinical investigation protocol, which may be transiently associated with the use of a medical product, regardless of whether or not it is considered to be related to the investigational product. A serious adverse event (SAE) is defined as any medical occurrence, resulting in death, or life-threatening, requiring hospitalization, resulting in impairment/disability, being a congenital anomaly, or all liver injuries grade 3 or higher , caused by drugs.

13. Bibliography

## **Statistical Analysis Plan**

### **General Considerations**

All abstracts and statistical analyzes will be provided for the intended **intention to treat population**, defined as all participants who are randomized to treatment. With the exception of the Primary Efficacy Parameter Analysis, percentage of responders for the intent-to-treat population, missing data will not be estimated or transported in any statistical analyzes.

All comparisons of treatment groups will be performed using two-tailed tests at a significance level of 0.05 ( $p < 0.05$ ). The null hypothesis for all analyzes is that there is no difference between the treatment groups.

All abstracts, statistical analyzes and individual record data of participants described below will be provided in separate annexes. Separate listings will be provided for each of the treatment groups in the intention-to-treat population.

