6.1. Primary outcome

- The primary study endpoint will be the all-cause mortality rate in the first year of therapy for critically ill participants starting ART.

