**Table 1 - Variables analyzed to determine comparability**

Variable	Analysis method
Basal age	One-way ANOVA/KW
Basal VL	One-way ANOVA/KW
CD4 + basal	One-way ANOVA/KW

The primary efficacy endpoint is the number (%) of participants who achieved the primary endpoint (HIV-1 Viral Load RNA <50 copies / ml) at week 48 (or discontinuation) visit. Participants will be counted as non-responders if they do not attend Week 48 (or term).

The DTG treatment group will be compared to the EFV group with respect to the percentage of responders using a chi-square test. Two-tailed, 95% confidence intervals for the percentage of responders will be calculated for each treatment group.

The following table identifies the secondary endpoints of effectiveness and the methods used to analyze them.

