### **Security Endpoints**

Summaries and statistical analyzes of safety parameters will be completed for the population by intention to treat. The incidence of at least one grade III or IV event will be the primary safety objective of the study. Treatment groups will be compared to the percentage of participants with at least one grade III or IV adverse event using a Chi-square test.

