### **Serious Adverse Events**

Secondary safety endpoints are the incidence of adverse events classified according to the preferred term and body system, the results of clinically significant laboratory tests and changes in vital signs. Treatment groups will be compared with the percentage of participants with clinically significant laboratory test results at Week 4, 8, 16, 24, 36 or 48 visits using Chi-square.

Summaries of physical examination data, vital signs (actual value and baseline change) and laboratory data (real value and change of baseline) will be provided at each visit.

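### Every group comparison is tested at two-sided 0.05 with no hierarchy and no nominal label, and conflicting primary endpoints leave no single test clearly carrying the 5% error

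*SAP*

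**What the plan says.** **Threshold.** SAP, General Considerations: "All comparisons of treatment groups will be performed using two-tailed tests at a significance level of 0.05". It adds: "The null hypothesis for all analyzes is that there is no difference between the treatment groups". Protocol 12.3 has the same rule. Neither document contains a hierarchy, an allocation of the error rate, a multiplicity adjustment, or a statement that any p-value is nominal.

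**Labels.** Protocol 6.1: "The primary study endpoint will be the all-cause mortality rate in the first year of therapy". Protocol 1.1 and 10.5 also put mortality first. The SAP, in the text after Table 1, differs: "The primary efficacy endpoint is the number (%) of participants who achieved the primary endpoint", which it specifies as viral load below 50 copies/ml at week 48. It introduces Table 2 with: "The following table identifies the secondary endpoints of effectiveness and the methods used to analyze them". That table includes the proportion of deaths. Protocol 12.5 matches the SAP here, so the protocol also disagrees with itself.

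**Safety.** SAP, Security Endpoints: "The incidence of at least one grade III or IV event will be the primary safety objective of the study". Under Serious Adverse Events, groups are also compared on the "percentage of participants with clinically significant laboratory test results at Week 4, 8, 16, 24, 36 or 48 visits using Chi-square".

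**Status.** Protocol 12.1: "This will be an exploratory pilot study".

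**The concern.** A 5% level describes one test. It describes a study's conclusion only if the plan says which test that conclusion rests on. Here the threshold is the same for all comparisons, and the two documents point to different tests as the main one.

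The clinical hypotheses in protocol section 2 cover CD4+ recovery, viral suppression and mortality, so a favourable p-value on any of the three could be presented as confirming the study's idea. Protocol section 14 plans 2 to 4 abstracts and at least 2 papers, so the choice of which result to feature will actually be made. At stake is whether a lone p<0.05, at one week or in one safety table, is read as an established difference between dolutegravir and efavirenz or as one of several exploratory results.

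**Working it through.** **1. The plan's own figure.** The documents give no count of tests and no study-wide error rate. The only design calculation is the sample size in protocol 12.1: mortality 2% versus 25%, 95% confidence, 80% power, 42 per arm. With mean rate 0.135 and difference 0.23:

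- Uncorrected: n = [1.960·√(2·0.135·0.865) + 0.842·√(0.02·0.98 + 0.25·0.75)]² / 0.23² = 33.4, rounded up to 34.
- With continuity correction: n' = (n/4)·[1 + √(1 + 4/(n·0.23))]² = 41.7, rounded up to 42.

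This reproduces 42 per arm (84 in total). The design was therefore sized for one two-sided 5% comparison, on mortality, with no allowance for other tests.

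**2. Counting the tests.** Protocol 10.1 schedules efavirenz viral load, CD4+ and laboratory data after baseline only at weeks 24 and 48, with adverse events collected over the 48 weeks.

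| Comparison | Source | Tests as listed | Tests on visits scheduled in both groups |
|---|---|---|---|
| Viral load <50 | Protocol 6.2; SAP primary and Table 2 | 5 weeks, plus week 48 again as primary = 6 | 2 (weeks 24, 48) |
| CD4+ | Protocol 6.2; SAP Table 2 | 2 | 2 |
| Deaths | SAP Table 2 | 1 | 1 |
| Any adverse event | SAP Table 2 | 1 | 1 |
| Grade III/IV event | SAP Security Endpoints | 1 | 1 |
| Laboratory results | SAP Serious Adverse Events | 6 | 1 if pooled, 2 if by visit |
| **Total** | | **17** | **8 to 9** |

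Of the 17, seven have no scheduled efavirenz data: viral load at weeks 4, 8 and 12, and laboratory results at weeks 4, 8, 16 and 36. That leaves 10. Counting week-48 viral load once leaves 9, and pooling the laboratory comparison leaves 8.

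**3. Chance of at least one p<0.05 with no true difference.** For k independent tests this is 1 − 0.95^k. For correlated tests it was computed from equicorrelated normal test statistics. The documents give no correlations, so those values are assumptions.

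| Tests | Independent | Correlation 0.5 | Correlation 0.7 |
|---|---|---|---|
| 2 (the competing primary efficacy endpoints) | 9.8% | 9.1% | 8.4% |
| 8 | 33.7% | 25.0% | 19.1% |
| 9 | 37.0% | 26.9% | 20.2% |

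If correlation is instead stronger within a marker than between markers (0.5 within and 0.2 between, or 0.7 and 0.3), 8 to 9 tests give about 28% to 34%, inside the range spanned by the table.

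**4. Sensitivity of the count.** It could be higher: the SAP also names an evaluable population, and laboratory results could be tested by analyte. Under independence the chance passes one half only at 14 tests (1 − 0.95^14 = 51.2%; for 13 tests, 48.7%).

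**The case against.** The strongest reply is that an exploratory pilot needs no multiplicity adjustment. That is right, and none is asked for here. The gap is that the exploratory status in protocol 12.1 never reaches the analysis rules, which speak only of significance at 0.05.

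A second reply is that the plan does rank its endpoints. This also stands in part. A reader might infer from the uniform threshold that all comparisons have equal standing; the documents do not support that, because they label primary and secondary endpoints for both efficacy and safety. The labels fail for a narrower reason: they disagree on which efficacy endpoint is primary, and they have no effect on the threshold.

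Third, a reader might count all 17 listed comparisons, obtain 1 − 0.95^17 = 58%, and call a false positive likely. That does not hold. Seven of those tests have no scheduled efavirenz data, one is the week-48 viral load counted again, and repeated measures in the same people are correlated.

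Fourth, mortality and week-48 response are linked by construction, since a participant who dies before week 48 does not attend and counts as a non-responder. The 10% for those two is therefore an upper figure.

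Finally, neither document states a rule for declaring success, so misuse of a lone p-value is a risk and not a stated intention.

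**Conclusion.** The concern holds in a limited form. All comparisons share a two-sided 0.05 threshold, nothing marks non-primary p-values as nominal, and the conflict over the primary efficacy endpoint means that no single test clearly carries the 5% error. The chance of at least one false positive is 34% to 37% for 8 to 9 independent tests and about 19% to 27% at assumed pairwise correlations of 0.7 to 0.5. That is well above 5% but below one half, so it is a substantial chance and not a likely event.

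The result rests on counting only visits scheduled in both groups, counting week-48 viral load once, and assumed correlations. It describes chance alone. The efavirenz group comes from chart review, so imbalance between the groups could produce differences that these percentages do not cover. The plan should be changed, but the point does not invalidate the study.

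**What to change.** Two linked changes are needed; the second alone would contradict the labels left in place.

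1. **Reconcile the primary endpoint.** In the SAP text around Tables 1 and 2, and in protocol 12.5, name first-year all-cause mortality as the primary efficacy endpoint. This matches protocol 6.1 and the sample-size basis in 12.1. Take the proportion of deaths out of the secondary table and move viral load below 50 copies/ml at week 48 into it. The missing-data exception in General Considerations is tied to the primary responder analysis, so reword it to name the analysis it covers.

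2. **Limit the significance statement.** In SAP General Considerations and protocol 12.3, replace the sentence on testing with:

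> The 0.05 significance statement applies only to the two-sided comparison of first-year all-cause mortality. All other efficacy and safety comparisons are exploratory and are reported as estimates with 95% confidence intervals; any p-value is nominal and is not described as significant.

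The cost is a few paragraphs of text in each document, plus confidence intervals for between-group differences, since the plan now promises intervals only for the responder percentage within each group. No data item, visit or participant is affected. The sponsor gives up significance claims on viral load, CD4+ and safety comparisons.
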